**Table 6 Maintenance Dose of GSK1278863**

Dose step	1	2	3	4	5	6	7	8
Dose level of GSK1278863 (once daily)	1 mg	2 mg	4 mg	6 mg	8 mg	12 mg	18 mg	24 mg
Number of GSK1278863 tablets taken	1 mg tablet ×1	2 mg tablet ×1	4 mg tablet ×1	6 mg tablet ×1	4 mg tablet ×2	6 mg tablet ×2	6 mg tablet ×3	6 mg tablet ×4

**Table 7 Dose Adjustment Algorithm (GSK1278863)**

Hgb (g/dL)	Hgb increase over 4 weeks (g/dL)	Treatment
>13.0	NA	Interrupt treatment until Hgb decreases to less than 12.5 g/dL Resume treatment at the one lower dose level (If interrupted at 1 mg: resume treatment at 1 mg once the one-step dose increase criteria are met)
12.5-13.0	NA	One-step dose reduction
11.5-12.5	>2.0 	One-step dose reduction
	≤2.0	Continue treatment at the current dose level
7.5-11.5	>2.0 	One-step dose reduction
	0.5-2.0	Continue treatment at the current dose level
	<0.5	One-step dose increase
<7.5	NA	Discontinue treatment permanently  and initiate another appropriate treatment

1) Cohort 3 only: At Week 4, if an Hgb increase of >1.0 g/dL over 2 weeks is observed, the dose of GSK1278863 will be reduced by one step; if an Hgb increase of ≤1.0 g/dL over 2 weeks is observed, treatment will be continued as specified in the dose adjustment algorithm other than one-step dose reduction for an Hgb increase of >2.0 g/dL over 4 weeks.

2): If an initial Hgb value is less than 7.5 g/dL, measurement will be repeated at the same study visit (using the same sample) to calculate the average. If the average meets the Hgb stopping criteria, study treatment will be permanently discontinued.

#### **6.4.2. Epoetin Beta Pegol (ND Subjects Only)**

For ND subjects (Cohort 1 and Cohort 3) randomized to the epoetin beta pegol group, ESA non-users and users will receive epoetin beta pegol subcutaneously according to the treatment regimens described below.

##### **6.4.2.1. Starting Dose for ESA Non-users**

ESA non-users will start subcutaneous treatment with epoetin beta pegol at a dose of 25 µg once every 2 weeks (Day 1). Dose adjustments will be made within the initial dose range of 25-150 µg (Table 8) according to the dose adjustment criteria (Table 9) to increase Hgb to 11.0 g/dL (lower limit of the target) or more based on the HemoCue Hgb value measured every 4 weeks. Dose changes will be made every 4 weeks. If any of the dose reduction criteria shown in Table 9 is met during treatment with epoetin beta pegol at 25 µg, treatment should be interrupted; once the dose reduction criteria are not met any longer, treatment will be resumed at a dose of 25 µg.

At Week 2, HemoCue Hgb value will be measured for subjects' safety confirmation. If the measurement shows an Hgb increase of  $>1.0$  g/dL over 2 weeks, the dose of epoetin beta pegol will be reduced by one step (or treatment interrupted) (Cohort 3 only).

**Table 8 Initial Dose of Epoetin Beta Pegol (ESA Non-users)**

Dose step	1	2	3	4	5
Dose level of epoetin beta pegol (once every 2 weeks)	25 µg	50 µg	75 µg	100 µg	150 µg

**Table 9 Initial Dose Adjustment Criteria for Epoetin Beta Pego (ESA Non-users)**

Hgb	Treatment
Hgb increase $<1.0$ g/dL over past 4 weeks, OR Hgb $<10.0$ g/dL and Hgb increase $\leq 2.0$ g/dL over past 4 weeks	One-step dose increase
Hgb increase $>2.0$ g/dL over past 4 weeks 	One-step dose reduction
Otherwise	Continue treatment at the current dose level

1) Cohort 3 only: Hgb increase of  $>1.0$  g/dL over past 2 weeks at Week 2.

Once Hgb increases to 11.0 g/dL or more, dose adjustments will be made according to the prespecified dose adjustment algorithm (Table 13). The dosing interval should be changed from once every 2 weeks to once every 4 weeks with dose conversion for dosing interval change (Table 10) after it is confirmed that all of the following criteria are met:

- Hgb in the target range (11.0-13.0 g/dL)
- Hgb change  $\leq 2.0$  g/dL over past 4 weeks
- Equivalent dose will be given twice (at least 4 weeks)

**Table 10 Dose Conversion of Epoetin Beta Pegol for Dosing Interval Change (ESA Non-users)**

Initial dose of epoetin beta pegol (given once every 2 weeks)		Dose conversion of epoetin beta pegol (given once every 4 weeks)
25 µg	→	50 µg
50 µg	→	100 µg
75 µg	→	150 µg
100 µg	→	200 µg
150 µg	→	250 µg

#### 6.4.2.2. Dose Conversion for ESA Users

For ESA users, prior ESA will be replaced with epoetin beta pegol at the equivalent dose once every 4 weeks (Day 1).

At Week 2, HemoCue Hgb value will be measured for subjects' safety confirmation. If the measurement shows an Hgb increase of  $>1.0$  g/dL over 2 weeks, the dose of GSK1278863 will be reduced by one step (or treatment interrupted) at Week 4 (Cohort 3 only).

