**Starting dose and dose adjustments of control (epoetin beta pegol)**

The starting dose and the dose adjustment algorithm for epoetin beta pegol are described in Section 6.4..

The starting dose of epoetin beta pegol for subjects not using ESA or subjects on epoetin was selected based on the Prescribing Information in Japan. For subjects on darbepoetin alfa, darbepoetin alfa will be switched to epoetin beta pegol at a dose ratio of 6:5 according to overseas Prescribing Information, given no specification for dose conversion from darbepoetin currently approved in Japan to epoetin beta pegol.

The dose adjustment algorithm for epoetin beta pegol was determined based on the product information and previous Japanese clinical studies. In Cohort 3, a study visit at Week 2 for Hgb monitoring was also added for the control group. (Refer to Section 6.4.2.)

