**Table 11 Replacement with Epoetin Beta Pegol-Initial Dose (ESA Users)**

Prior ESA		Epoetin beta pegol
Epoetin	<4500 IU per week	100 µg once every 4 weeks
	≥4500 IU per week	150 µg once every 4 weeks
Darbepoetin alfa	30 µg once every 4 weeks *	25 µg once every 4 weeks
	60 µg once every 4 weeks *	50 µg once every 4 weeks
	90 µg once every 4 weeks *	75 µg once every 4 weeks
	120 µg once every 4 weeks *	100 µg once every 4 weeks
	180 µg once every 4 weeks *	150 µg once every 4 weeks
Epoetin beta pegol	25, 50, 75, 100, 150, 200, 250 µg once every 4 weeks *	25, 50, 75, 100, 150, 200, 250 µg once every 4 weeks

\*: Allowance of ±1 week

Maintenance treatment will be started at Week 4 as described in Section 6.4.2.3.

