#### 6.4.2.3. Maintenance Dose (ESA Non-users and Users)

Epoetin beta pegol will be administered once every 4 weeks from dosing interval change (once every 4 weeks) with Hgb ≥11.0 g/dL to Week 52 in ESA non-users and from Weeks 4 to 52 in ESA users. Interruption of treatment or dose adjustments will be made within the maintenance dose range of 25-250 µg (Table 12) according to the dose adjustment algorithm (Table 13) to achieve and/or maintain Hgb within the target range (11.0-13.0 g/dL) based on the HemoCue Hgb value measured every 4 weeks. If any of the one-step dose reduction criteria is met during treatment at the minimum maintenance dose (25 µg), treatment should be interrupted; once the one-step dose reduction criteria are not met any longer, treatment at 25 µg will be resumed. If the one-step dose increase criterion is met during treatment at the maximum maintenance dose (250 µg), treatment at 250 µg should be continued.

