**Table 13 Dose Adjustment Algorithm (Epoetin Beta Pegol)**

Hgb	Hgb increase over 4 weeks	Treatment
-----	---------------------------	-----------

(g/dL)	(g/dL)	
>13.0	NA	Interrupt treatment until Hgb decreases to less than 12.5 g/dL Resume treatment at the one lower dose level (resume treatment at 25 µg if interrupted at 25 µg)
12.5-13.0	NA	One-step dose reduction
11.5-<12.5	>2.0	One-step dose reduction
	≤2.0	Continue treatment at the current dose level
7.5-<11.5	>2.0	One-step dose reduction
	1.0-2.0	Continue treatment at the current dose level
	<1.0	One-step dose increase
<7.5	NA	Discontinue treatment permanently * and initiate another appropriate treatment

\*: If an initial Hgb value is less than 7.5 g/dL, measurement will be repeated at the same study visit (using the same sample) to calculate the average. If the average meets the Hgb stopping criteria, study treatment will be permanently discontinued.

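### The Week 2 safety rule for control-arm ESA users names the wrong drug, and once corrected it still clashes with Table 13 at Week 4

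*Protocol*

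**What the plan says.** Section 6.4.2 sets out dosing "For ND subjects (Cohort 1 and Cohort 3) randomized to the epoetin beta pegol group". Within it, Section 6.4.2.2 switches ESA users to epoetin beta pegol every 4 weeks from Day 1. It then adds a Cohort 3 check: if the Week 2 HemoCue value shows a rise above 1.0 g/dL over 2 weeks, "the dose of GSK1278863 will be reduced by one step (or treatment interrupted) at Week 4 (Cohort 3 only").

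The matching rule for control-arm ESA non-users, in Section 6.4.2.1, says "the dose of epoetin beta pegol will be reduced by one step (or treatment interrupted) (Cohort 3 only"). Section 4.5 confirms that the control arm was meant to have the check: "In Cohort 3, a study visit at Week 2 for Hgb monitoring was also added for the control group".

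For the Week 4 dose in ESA users, the line under Table 11 says "Maintenance treatment will be started at Week 4 as described in Section 6.4.2.3". Section 6.4.2.3 then applies Table 13, "based on the HemoCue Hgb value measured every 4 weeks". The only footnote to Table 13 concerns the stopping rule below 7.5 g/dL.

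This is the current Amendment 4 text. The Amendment 3 text bound in the same document has the same wording in Section 6.4.2.2.

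**The concern.** There are two faults, and mending the first does not mend the second.

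First, the rule tells the site to reduce a drug the subject is not receiving. It is not a rule for the other arm put in the wrong place, because Section 6.4.1.1 already gives the GSK1278863 arm its own Week 2 rule.

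Second, once the name is corrected, two instructions govern one injection. Section 6.4.2.2 uses the rise from Day 1 to Week 2. Table 13 uses the Week 4 value and the rise from Day 1 to Week 4, with no reference to Week 2. A subject who tripped the rapid-rise safeguard could have the dose held, or even raised, by a site that follows Table 13 correctly. Section 4.5 ties the limits on rate of rise to preventing adverse reactions, and Section 7 allows waivers only for immediate safety concerns, so the text sites work from needs to be executable and unambiguous.

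**Working it through.** The plan gives no figure to reproduce here. The check sets the two rules side by side, with epoetin beta pegol substituted in Section 6.4.2.2.

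**Inputs**
- Section 6.4.2.2, corrected: rise from Day 1 to Week 2 above 1.0 g/dL means reduce one step (or interrupt) at Week 4.
- Table 13: above 13.0, interrupt; 12.5 to 13.0, reduce; 11.5 to below 12.5, reduce if the 4-week rise exceeds 2.0, otherwise continue; 7.5 to below 11.5, reduce if the rise exceeds 2.0, continue if 1.0 to 2.0, increase if below 1.0; below 7.5, discontinue.
- Table 12 steps: 25, 50, 75, 100, 150, 200, 250 µg.
- ESA-user entry range (Section 5.1): 9.0 to 13.0 g/dL.

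**Worked subjects** (hypothetical, all triggering with a Week 2 rise of 1.2 g/dL)

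| Day 1 | Week 2 | Week 4 | 4-week rise | 6.4.2.2 | Table 13 |
|---|---|---|---|---|---|
| 10.5 | 11.7 | 12.0 | 1.5 | reduce | continue |
| 10.5 | 11.7 | 11.0 | 0.5 | reduce | increase |
| 9.5 | 10.7 | 11.0 | 1.5 | reduce | continue |
| 11.5 | 12.7 | 12.6 | 1.1 | reduce | reduce |
| 9.2 | 10.4 | 11.4 | 2.2 | reduce | reduce |
| 12.0 | 13.2 | 13.1 | 1.1 | reduce or interrupt | interrupt |

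The rules differ in three Table 13 cells: 7.5 to below 11.5 with a rise below 1.0 (reduce against increase), the same band with a rise of 1.0 to 2.0 (reduce against continue), and 11.5 to below 12.5 with a rise of at most 2.0 (reduce against continue). All three can be reached from the entry range. The rules agree at 12.5 to 13.0, and below 12.5 wherever the 4-week rise exceeds 2.0.

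**How Table 13 divides the Week 4 values of a triggered subject**
- Day 1 at 10.5: increase at 7.5–11.4, continue at 11.5–12.4, reduce at 12.5–13.0.
- Day 1 at 9.0: increase at 7.5–9.9, continue at 10.0–11.0, reduce at 11.1–13.0.

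**Dose at stake, reduce against increase**
- From 100 µg (for example, converted from darbepoetin alfa 120 µg in Table 11): 75 against 150 µg, 150/75 = 2.0-fold; continuing gives 100 µg.
- From 50 µg: 25 against 75 µg, 75/25 = 3.0-fold.
- From 25 µg: interruption against 50 µg.

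**Subjects covered.** Cohort 3 is planned at 117 with at least 80 ESA non-users (Table 1), so at most 117 − 80 = 37 ESA users. At 1:1, 37/2 = 18.5, or about 18 in the control arm. The protocol does not say how many would rise by more than 1.0 g/dL by Week 2.

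**The case against.** The drug name corrects itself: the section covers only epoetin beta pegol subjects, the preceding sentence names that drug, and no site could follow the literal text. That is fair as to intent. It does not excuse an error in an operative dosing rule.

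The stronger objection is that a specific rule overrides a general one. Section 6.4.2.2 is confined to one cohort, one trigger and one visit; if Table 13 prevailed at Week 4, the rule would have no effect of its own. This is the likely intention, but the protocol states it nowhere. Elsewhere the authors wrote the 2-week criterion into the dosing table itself: Table 9 has a Cohort 3 footnote ("over past 2 weeks at Week 2"), and a Table 7 footnote says how a 2-week rise enters the Week 4 decision for GSK1278863. Table 13 has neither a footnote nor a pointer back.

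Three points on size stand:
- The lower end of the increase band is unrealistic. A triggered subject starting at 10.5 is at 11.6 or more at Week 2, so reaching 7.5 at Week 4 needs a fall of at least 11.6 − 7.5 = 4.1 g/dL in 2 weeks.
- In the 10.5, 11.7, 11.0 case most of the rise has reversed, and raising the dose there is not shown to be unsafe.
- Section 4.5 reports that the excess of Week 4 rises above 2.0 g/dL was not seen in ND ESA users. That is a different threshold and visit, but it suggests few will trigger.

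**Conclusion.** The plan is wrong as written on both counts. The wrong drug is certain from the text; that epoetin beta pegol was meant is an inference, but a strong one. The Week 4 clash after correction is real in three Table 13 cells, and no stated precedence resolves it.

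The consequence is limited. At most about 18 control subjects are covered, assuming Cohort 3 enrols as planned and splits evenly, and only those with a Week 2 rise above 1.0 g/dL are affected. For them, one dose can differ two- to three-fold between the rules at the 100 µg and 50 µg levels. No effect on Week 4 hemoglobin or on the Weeks 40 to 52 endpoints is claimed. It should be fixed because it is a safety dosing instruction, not because it threatens the non-inferiority comparison.

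**What to change.** In Section 6.4.2.2, replace GSK1278863 with epoetin beta pegol. Add a Table 13 footnote for Cohort 3 ESA users, to this effect: where hemoglobin rose by more than 1.0 g/dL from Day 1 to Week 2, reduce one step at Week 4 (interrupt if on 25 µg), in place of the continue and increase rows. Interruption above 13.0 g/dL and discontinuation below 7.5 g/dL still apply, and the step does not add to a reduction that Table 13 already orders.

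This gives effect to the unconditional reduction the section already contains. The sponsor should confirm that it is still wanted when hemoglobin has fallen back well below target by Week 4 (for example 10.5, 11.7, 9.5). If not, the footnote should say so.

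The cost is one drug name, one footnote and a memo to sites. Sample size and analysis are unchanged.

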**Table 11 Replacement with Epoetin Beta Pegol-Initial Dose (ESA Users)**

Prior ESA		Epoetin beta pegol
Epoetin	<4500 IU per week	100 µg once every 4 weeks
	≥4500 IU per week	150 µg once every 4 weeks
Darbepoetin alfa	30 µg once every 4 weeks *	25 µg once every 4 weeks
	60 µg once every 4 weeks *	50 µg once every 4 weeks
	90 µg once every 4 weeks *	75 µg once every 4 weeks
	120 µg once every 4 weeks *	100 µg once every 4 weeks
	180 µg once every 4 weeks *	150 µg once every 4 weeks
Epoetin beta pegol	25, 50, 75, 100, 150, 200, 250 µg once every 4 weeks *	25, 50, 75, 100, 150, 200, 250 µg once every 4 weeks

\*: Allowance of ±1 week

Maintenance treatment will be started at Week 4 as described in Section 6.4.2.3.

#### 6.4.2.3. Maintenance Dose (ESA Non-users and Users)

Epoetin beta pegol will be administered once every 4 weeks from dosing interval change (once every 4 weeks) with Hgb ≥11.0 g/dL to Week 52 in ESA non-users and from Weeks 4 to 52 in ESA users. Interruption of treatment or dose adjustments will be made within the maintenance dose range of 25-250 µg (Table 12) according to the dose adjustment algorithm (Table 13) to achieve and/or maintain Hgb within the target range (11.0-13.0 g/dL) based on the HemoCue Hgb value measured every 4 weeks. If any of the one-step dose reduction criteria is met during treatment at the minimum maintenance dose (25 µg), treatment should be interrupted; once the one-step dose reduction criteria are not met any longer, treatment at 25 µg will be resumed. If the one-step dose increase criterion is met during treatment at the maximum maintenance dose (250 µg), treatment at 250 µg should be continued.

**Table 12 Maintenance Dose of Epoetin Beta Pegol**

Dose step	1	2	3	4	5	6	7
Epoetin beta pegol (once every 4 weeks)	25 µg	50 µg	75 µg	100 µg	150 µg	200 µg	250 µg

**Table 13 Dose Adjustment Algorithm (Epoetin Beta Pegol)**

Hgb	Hgb increase over 4 weeks	Treatment
-----	---------------------------	-----------

(g/dL)	(g/dL)	
>13.0	NA	Interrupt treatment until Hgb decreases to less than 12.5 g/dL Resume treatment at the one lower dose level (resume treatment at 25 µg if interrupted at 25 µg)
12.5-13.0	NA	One-step dose reduction
11.5-<12.5	>2.0	One-step dose reduction
	≤2.0	Continue treatment at the current dose level
7.5-<11.5	>2.0	One-step dose reduction
	1.0-2.0	Continue treatment at the current dose level
	<1.0	One-step dose increase
<7.5	NA	Discontinue treatment permanently * and initiate another appropriate treatment

\*: If an initial Hgb value is less than 7.5 g/dL, measurement will be repeated at the same study visit (using the same sample) to calculate the average. If the average meets the Hgb stopping criteria, study treatment will be permanently discontinued.

## 6.5. Blinding

This is an open-label study.

## 6.6. Packaging and Labeling

The contents of the label will be in accordance with all applicable regulatory requirements.

## 6.7. Preparation/Handling/Storage/Accountability

- No special preparation of study treatment is required.
- Only subjects enrolled in the study may receive study treatment and only authorized site staff may supply or administer study treatment. All study medications must be stored in a secure environmentally controlled and monitored (manual or automated) area in accordance with the labeled storage conditions with access limited to the investigator (or subinvestigator) and authorized site staff.
- Subjects must bring all of supplied study medication bottles of GSK127886 at each study visit. Study staff will collect all of study medication bottles supplied at the previous study visit and supply new study medication bottles.
- The investigator (or subinvestigator), institution, or the head of the medical institution (where applicable) is responsible for study treatment accountability, reconciliation, and record maintenance (i.e. receipt, reconciliation and final disposition records).
- Under normal conditions of handling and administration, study medication is not expected to pose significant safety risks to site staff. GSK will provide a document describing occupational hazards and recommended handling precautions either to the investigator (or subinvestigator) when necessary or upon request of the medical institution.
- Further details are provided in the SRM.

## **6.8. Compliance with Study Treatment Administration**

### **GSK1278863**

Since GSK1278863 is self-administered, compliance with GSK1278863 treatment will be assessed through an interview with subjects at each study visit and recorded in the source document and eCRF. A record of the number of GSK1278863 tablets dispensed to and taken by each subject will be maintained and reconciled with study treatment and compliance records. In addition, the number of GSK1278863 doses dispensed, used, and unused, as well as study treatment start and stop dates will be recorded in the eCRF (the number of doses returned and unreturned will also be recorded separately).

### **Epoetin beta pegol**

Epoetin beta pegol will be subcutaneously administered to subjects at the site. Dosing details will be recorded in the source document and eCRF.

## **6.9. Treatment of Study Treatment Overdose**

For the purposes of this study, an overdose of GSK1278863 is defined as any dose greater than the highest daily dose included in the protocol. There is no specific antidote for overdose with GSK1278863. The expected manifestations of GSK1278863 overdosage include signs and symptoms associated with an excessive and/or rapid increase in Hgb concentration. GSK1278863 is highly protein bound; thus, clearance of GSK1278863 by hemodialysis or peritoneal dialysis is very low and these are not effective methods to enhance the elimination of GSK1278863. GSK1278863 metabolites are, in part, cleared via hemodialysis. In the event of a suspected overdose, it is recommended that the appropriate supportive clinical care be instituted, as dictated by the subject's clinical status. Additionally, subjects should be monitored closely for cardiovascular events, increased heart rate and hematologic abnormalities.

Consult the respective approved Prescribing Information for information on overdose for epoetin beta pegol.

## **6.10. Treatment after the End of the Study**

Since the target disease studied is not life-threatening or severely debilitating and there is the alternative therapy, subjects will not receive any additional treatment from GSK after completion of the study. Regardless of whether the sponsor provides specific treatments at the completion of the study, the investigator (or subinvestigator) is responsible for ensuring that consideration has been given to post-study care of the subject's medical condition.

## **6.11. Concomitant Medications and Non-Drug Therapies**

Concomitant medications, including over-the-counter medications and supplements, taken during the study will be recorded in the eCRF. Drug names and start/stop dates will be recorded for general concomitant medications, while additional details, including dose, route of administration, and dosing frequency, will be recorded for certain medications (e.g., ESAs, iron, anti-hypertensive medications). Further details are provided in the SRM.

### **6.11.1. Permitted Medications and Non-Drug Therapies**

Unless specified as a prohibited medication in Section 6.11.2., all concomitant medications should be considered permitted provided they are not contraindicated for the individual subject concerned.

Regular multivitamins (at recommended daily allowance) and other supplements such as calcium and vitamin D may be used if permitted by the investigator or his/her designee.

CYP2C8 is involved in the primary route of metabolism of GSK1278863. Accordingly, co-administration of GSK1278863 with moderate CYP2C8 inhibitors (e.g., clopidogrel, teriflunomide, deferasirox) should be performed with caution. If one of these medications is started, stopped or the dose is changed, Hgb should be monitored every 4 weeks for 12 weeks using a point-of-care Hgb analyzer.

Antihyperphosphatemic agents containing iron (e.g., ferric citrate hydrate) may be started from Week 4 onwards unless any other antihyperphosphatemic agents are appropriate. Once started, iron-containing antihyperphosphatemic agents must be continued until the end of the study wherever possible.

